### 9.1.2 Serious Adverse Events

An SAE is an untoward medical occurrence or effect associated with the use of a study drug at any dose, regardless of whether it is considered to be related to the study drug, which results in one of the following:

- Death (i.e., all deaths on treatment or within 4 weeks after last study drug administration), including deaths due to disease progression. Any death occurring later than 4 weeks following the last dose need not be reported as an SAE unless it is a result of an event that started within the period covered by the on-study definition. The reported adverse event should be the event that caused the death. In addition, any adverse event resulting in death that occurs subsequent to the adverse event-reporting period and that the investigator assesses as possibly related to the study drug should also be reported as serious.
- Life-threatening adverse event. This is an event that, in the view of either the investigator or the sponsor, places the subject at immediate risk of death. It does not include an event that, had it occurred in a more severe form, hypothetically might have caused death.
- Inpatient hospitalization or prolongation of existing hospitalization (e.g., excluding hospitalizations for administration of the study drug, procedures required by the study protocol, or aniridia-related diagnostic procedures; other planned hospitalizations; or hospitalizations related only to progression of disease). Treatments in the emergency room for procedures such as hydration that do not require admitting the subject to the hospital and observational durations in the emergency room for less than 24 hours are not considered serious.
- Persistent or significant disability or incapacity or substantial disruption of the ability to conduct normal life functions, not related to aniridia.
- Any other medically important event that the investigator or the sponsor judges to be serious or which is defined as serious by the regulatory agency in the local country. Medical judgment should be exercised in deciding whether a reaction is serious in other situations. Important medical events that do not result in death, are not immediately life-threatening, and do not require hospitalization may be considered serious when, based on appropriate medical judgment, they may jeopardize the subject and may require medical or surgical intervention to prevent any of the outcomes listed above. Examples of such medical events include allergic bronchospasm requiring intensive treatment administration in an

emergency room or at home, newly diagnosed malignancy, or blood dyscrasias, or convulsions that do not result in inpatient hospitalization, or the development of drug dependency or drug abuse.

- A pregnancy resulting in spontaneous abortion, stillbirth, neonatal death, or congenital anomaly [including that in an aborted fetus]).

An event need not be reported as a SAE if it exclusively represents a relapse or an expected change or progression of the baseline aniridia. This type of event need only to be reported as an adverse event.

Note that any SAEs occurring after the end of the subject's participation in the study should be reported to the sponsor if the investigator becomes aware of them.

### **9.1.3 Unexpected Adverse Events**

Unexpected adverse events are defined as those events that were not previously reported with study drug as referenced in the most current investigator's brochure, or that are symptomatically and pathophysiologically related to a known toxicity but differ because of greater severity or specificity. For example, under this definition, hepatic necrosis would be unexpected (by virtue of greater severity) if the investigator's brochure only referred to elevated hepatic enzymes or hepatitis. Similarly, cerebral thromboembolism and cerebral vasculitis would be unexpected (by virtue of greater specificity) if the investigator brochure only listed cerebral vascular accidents. "Unexpected," as used in this definition, also refers to an adverse event that is mentioned in the most current investigator's brochure as occurring with the class of drugs or as anticipated from the pharmacological properties of the study drug but is not specifically mentioned as occurring with the medicinal product.

For the purposes of considering expectedness, the ataluren investigator's brochure provides a summary of the safety profile of ataluren based on available clinical information (also referred to as the reference safety information).

## **9.2 Eliciting Adverse Event Information**

The investigator is to report all directly observed adverse events and all adverse events spontaneously reported by the study subject or parent/guardian in case of a child. In addition, each study subject will be questioned about adverse events at each scheduled clinic visit after study drug administration or during any telephone contact with the subject or parent/guardian in case of a child. The type of question asked should be open-ended, e.g., "*How has your child been feeling?*" or a similar type of query.

## **9.3 Adverse Event Recording**

All adverse events (both serious and non-serious) that occur in subjects during the adverse event reporting period must be recorded, whether or not the event is considered drug related. In addition, any known untoward event that occurs subsequent to the adverse event reporting period that the investigator assesses as possibly related to the investigational drug/product should also be recorded as an adverse event.

All adverse events are to be recorded in the source documents and on the eCRF using concise medical terminology; whenever possible terms contained in the Medical Dictionary for Regulatory Activities (MedDRA) should be employed. In addition, the following information should be recorded:

- Indication of whether the event is serious or non-serious (see Section 9.1.2)
- Relationship to study drug (see Section 9.4)
- Severity of the event (see Section 9.5)
- Onset date
- Resolution date, or date of death
- Action taken
- Outcome of the event

Classification of the event as serious or non-serious determines the reporting procedures to be followed.

#### 9.4 Describing Adverse Event Relationship to Study Drug

Based on the considerations outlined in Table 4 the investigator should provide an assessment of the relationship of the adverse event to the study drug, i.e., whether there is a reasonable possibility that the study drug caused the adverse event.

**Table 4. Relationship of Study Drug to Adverse Event**

Relationship	Description
Probable	A clinical event in which a relationship to the study drug seems probable because of such factors as consistency with known effects of the drug; a clear temporal association with the use of the drug; improvement upon withdrawal of the drug; recurrence upon re-challenge with the drug; lack of alternative explanations for the event.
Possible	A clinical event occurring coincident with administration of the study drug and which may or may not be explained by concurrent disease or other drugs or chemicals. Information on drug withdrawal or re-challenge may be lacking.
Unlikely	A clinical event with a temporal relationship to the study drug exposure that does not preclude causality but for which there is a clear alternate cause that is more likely to have caused the adverse event than study drug. Such alternatives include a concomitantly administered drug, the subject's disease state, other medical conditions, or environmental factors.
Unrelated	A clinical event, for which a relationship to the study drug seems improbable because of factors such as inconsistency with known effects of the study drug, lack of a temporal association with study drug administration, lack of association of the event with study drug withdrawal or re-challenge, and/or presence of alternative explanations for the event. Alternative explanations might include a known relationship of the adverse event to a concomitant drug, medical history of a similar event, the subject's disease state, other medical conditions, or environmental factors.

## 9.5 Grading of Severity of Adverse Events

The severity of adverse events will be graded using the CTCAE Version 4.0 (refer to the Study Manual). For each episode, the highest severity grade attained should be reported.

If a CTCAE criterion does not exist, the investigator should use the grade or adjectives: Grade 1 (mild), Grade 2 (moderate), Grade 3 (severe), Grade 4 (life-threatening), or Grade 5 (fatal) to describe the maximum intensity of the adverse event. For purposes of consistency with the CTCAE, these intensity grades are defined in Table 5.

**Table 5. Grading of Adverse Event Severity**

Grade	Adjective	Description
Grade 1	Mild	Sign or symptom is present, but it is easily tolerated, is not expected to have a clinically significant effect on the subject's overall health and well-being, does not interfere with the subject's usual function, and is not likely to require medical attention
Grade 2	Moderate	Sign or symptom causes interference with usual activity or affects clinical status, and may require medical intervention
Grade 3	Severe	Sign or symptom is incapacitating or significantly affects clinical status and likely requires medical intervention and/or close follow up
Grade 4	Life-threatening	Sign or symptom results in a potential threat to life
Grade 5	Fatal	Sign or symptom results in death

Note the distinction between the seriousness and the severity of an adverse event. Severity is a measure of intensity; thus, a severe reaction is not necessarily a serious reaction. For example, a headache may be severe in intensity, but would not be classified as serious unless it met one of the criteria for serious events listed in Section 9.2.

## 9.6 Pregnancy

PTC Therapeutics should be notified in the event that a female subject in the study becomes pregnant at any time after the subject's first dose of study drug. Any such pregnancy occurring on-study or within 60 days of the last administration of study drug must be reported on a Pregnancy Notification Form (see Study Manual for details). This must be done whether or not an adverse event has occurred and within 24 hours of awareness of the pregnancy. The information submitted should include the anticipated date of birth or pregnancy termination.

If possible, the investigator should follow the subject until completion of the pregnancy and notify the PTC Therapeutics medical monitor or designee of the outcome within 5 days or as specified below. The investigator will provide this information as a follow up to the initial Pregnancy Notification Form via the Pregnancy Outcome Form (see the Study Manual for details).

If the outcome of the pregnancy meets the criteria for immediate classification as an SAE (i.e., spontaneous abortion, stillbirth, neonatal death, or congenital anomaly [including that in an aborted fetus]), the investigator should follow the procedures for reporting SAEs, i.e., report the event to the PTC Therapeutics Safety Department or designee and follow up by submission of appropriate adverse event eCRFs (see Section 9.8).

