### 4.2 Inclusion Criteria

Subjects who will be selected for this study must meet the following criteria:

1. Evidence of signed and dated informed consent document(s) indicating that the study candidate (and/or a parent/legal guardian) has been informed of all pertinent aspects of the study. *Note: If the study candidate is considered a child under local regulation, a parent or legal guardian must provide written consent prior to initiation of study screening procedures and the study candidate may be required to provide written assent. The rules of the responsible institutional review board/independent ethics committee (IRB/IEC) regarding whether one or both parents must provide consent and the appropriate ages for obtaining consent and assent from the subject should be followed.*
2. Age  $\geq 2$  years and of either gender.
3. Body weight  $\geq 12$  kg.
4. Documentation of the presence of a nonsense mutation in 1 allele of the PAX6 gene as determined by genotyping performed at a laboratory certified by the College of American Pathologists (CAP), or under the Clinical Laboratory Improvement Act/Amendment (CLIA), or by an equivalent organization. *Note: Sponsor review of the genotyping documentation is required.*
5. Clinical diagnosis of aniridia.
6. Willingness and ability to comply with scheduled visits, drug administration plan, study procedures, and study restrictions.
7. Good general health, as determined at Visit 1 (Screening) by medical history and physical examination (including vital sign measurements).
8. No clinically significant abnormality based upon laboratory assessments at Visit 1 (Screening), in the opinion of the investigator.

9. Female subjects of childbearing potential are eligible for the study but must be willing to use adequate (at least 1 form of) contraceptive methods as described below during the study treatment period (starting from the day of first dose of study drug and ending 60 days after the last dose of study drug). Childbearing potential is defined as subjects who have experienced menarche and who are neither postmenopausal nor have been permanently sterilized.
  - Hormonal methods of contraception (including oral and transdermal contraceptives, injectable progesterone, progestin subdermal implants, progesterone-releasing intrauterine devices [IUDs]) initiated at least 14 days prior to the first dose of study drug
  - Abstinence
  - Placement of a copper-containing IUD

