  - Condom with spermicidal foam/gel/film/cream/suppository
  - Postmenopausal at least 12 months prior to first dose of study drug or permanently sterilized (e.g., tubal occlusion, hysterectomy, bilateral salpingectomy)
  - Male partner who has had a vasectomy for at least 3 months prior to the first dose of study drug
10. Male subjects with partners of childbearing potential must agree to use adequate (at least 1 form of) contraception as described below during the study treatment period (starting from the day of first dose of study drug and ending 60 days after the last dose of study drug).
  - Abstinence
  - Vasectomy for at least 3 months prior to first dose of study drug or surgically sterile
  - Without a vasectomy, must use a condom with spermicidal foam/gel/film/cream suppository

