## **6.2 Study Drug Treatment**

### **6.2.1 Stratification and Randomization**

After a subject has completed the necessary screening assessments and has been confirmed to be eligible by the investigator, the subject can be randomized into the study.

During Stage 1, a minimum of 36 eligible subjects will be stratified by age group ( $\leq 10$  years old versus  $>10$  years old) and then be randomized in a 2:1 ratio to 1 of 2 possible treatment assignments:

- Ataluren (10, 10, 20 mg/kg)
- Placebo

The first dose of study drug will be administered in the clinic and the date and time of administration will be recorded. At the end of each Stage, the last dose of study drug will be taken on the evening before the clinic visit (i.e., the night before the Visit 4/Week 48 [end of Stage 1], the night before Visit 8 (EOS/ET)/Week 144 [end of Stage 2], and the night before Visit 12 (end of Sub-study)/Week 240).

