## 8.2 Visit 8 (Week 144±28 Days – End of Treatment/Start of Sub-study)

The subject will return to the site for Visit 8 (Week 144). Additionally, any subject who discontinues early from the parent study should complete the Visit 8 assessments and return in 4 weeks for follow-up assessments.

This visit will be considered the end of the parent study and the beginning of the sub-study. Subjects should have taken their final dose of study drug for the parent study the night before the clinic visit.

Visit 8 will proceed as follows:

- Record any adverse events occurring since last visit and any that occur during this visit
- Record any changes in concomitant medications
- Collect any unused study drug
- Study Drug Dosing Diary review and collection: The diary will be collected and reviewed
- Physical examination
- Height and weight
- Vital signs (including systolic and diastolic blood pressure, radial pulse rate, and body temperature): performed after the subject has been in a sitting position for 3 - 5 minutes
- Complete the following ophthalmological assessments:
  - [REDACTED]
  - Ophthalmoscopy examination
  - BCVA and refraction
  - Slit-lamp examination - Slit-lamp examination should precede [REDACTED] measurement.
  - Slit-lamp photography. The Reading Center manual should be referenced for detailed instructions regarding macro photography.
  - OCT/Fundus photography - Anterior and posterior segment OCT and fundus photography will be performed. The Reading Center manual should be referenced for detailed instructions.
  - Humphrey visual fields
  - [REDACTED]

- [REDACTED]
- MNREAD
- Blood draw for clinical laboratory evaluations:
  - Hematology and biochemistry
  - Serum  $\beta$ -HCG, as applicable (sample taken only for female subjects of childbearing potential)
  - [REDACTED]
- Urinalysis
- No study drug will be dispensed at this visit for subjects that do not consent to the sub-study. Subjects not continuing into the sub-study should return to the clinic in 4-weeks ( $\pm 7$  days) for their Follow-up visit.

For all subjects that choose to participate in the open-label sub-study, in addition to the Visit 8 assessments listed above, the following will need to be completed:

- Obtain written informed consent/assent
- Dispense open-label ataluren and Study Drug Dosing Diary, and review administration instructions
  - TID dosing 10 mg/kg, 10 mg/kg, 20 mg/kg (morning, midday, evening)
- Schedule Visit 9 in 24 weeks  $\pm 28$  days

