**8.2.1.2 Visit 12 (Week 240  $\pm$ 28 Days – End of Study/Early Termination Visit)**

This visit will be considered the end of sub-study and should be completed for all subjects. Subjects participating in the sub-study who terminate the study before Visit 12 should complete the Visit 12 assessments at the time of early termination. Subjects should take their final dose of study drug the night before the clinic visit.

Visit 12, End of Study/Early Termination Visit will proceed as follows:

- Record any adverse events occurring since last visit and any that occur during this visit
- Record any changes in concomitant medications
- Collect any unused study drug
- Study Drug Dosing Diary review and collection: The diary will be collected and reviewed
- Height and weight
- Vital signs (including systolic and diastolic blood pressure, radial pulse rate, and body temperature): performed after the subject has been in a sitting position for 3 - 5 minutes
- Complete the following ophthalmological assessments:
  - Ophthalmoscopy examination
  - BCVA and refraction
  - [REDACTED]
  - MNREAD
  - Humphrey visual fields
- Blood draw for clinical laboratory evaluations:

- Hematology and biochemistry
- Serum  $\beta$ -HCG, as applicable (sample taken only for female subjects of childbearing potential)
- Urinalysis
- No study drug will be dispensed at this visit
- Schedule Follow-up Visit in 4 weeks  $\pm$ 7 days

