#### **8.2.1.3 Follow-up Visit (4 Weeks Post End of Study/Early Termination Visit $\pm$ 7 Days)**

Follow-up should occur 4 weeks ( $\pm$ 7 days) after the End of Study/Early Termination visit. Additionally, any subject who discontinues early from the parent study or the sub-study should complete this visit. The Follow-up visit will proceed as follows:

- Record any adverse events occurring since last visit and any that occur during this visit
- Record any changes in concomitant medications
- Physical examination
- Height and weight
- Vital signs (including systolic and diastolic blood pressure, radial pulse rate, and body temperature): performed after the subject has been in a sitting position for 3 – 5 minutes
- Complete the following ophthalmological assessments:
  - Ophthalmoscopy examination
- Blood draw for clinical laboratory evaluations
  - Hematology and biochemistry
- Urinalysis

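### Minor: the 4-week follow-up visit draws blood but includes no beta-HCG, so a conception in the last days of dosing meets no later scheduled pregnancy test

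*Protocol*

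**What the plan says.** **How long pregnancy matters to the plan.** Protocol 4.2, criterion 9, requires contraception from female subjects of childbearing potential "starting from the day of first dose of study drug and ending 60 days after the last dose of study drug". Protocol 9.6 sets the same end for reporting: "Any such pregnancy occurring on-study or within 60 days of the last administration of study drug must be reported on a Pregnancy Notification Form". The form is due within 24 hours of the site learning of the pregnancy.

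**When dosing ends.** Protocol 6.2.1: "At the end of each Stage, the last dose of study drug will be taken on the evening before the clinic visit". Section 8.2 repeats this for Visit 8 ("Subjects should have taken their final dose of study drug for the parent study the night before the clinic visit") and Section 8.2.1.2 for Visit 12 ("Subjects should take their final dose of study drug the night before the clinic visit").

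**When pregnancy is tested.** Serum beta-HCG is listed at screening, at baseline and at every treatment visit up to Visit 8, or up to Visit 12 in the sub-study.

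**What happens at follow-up.** Section 8.2.1.3 lists "Blood draw for clinical laboratory evaluations", and under it only hematology and biochemistry, followed by urinalysis. In Protocol Tables 2 and 3 the laboratory row continues into the follow-up column and the beta-HCG row does not. The SAP's Appendix A tables also schedule no beta-HCG at follow-up. The panels defined in Protocol 8.3.7, 8.3.8 and 8.3.10 contain no pregnancy test.

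**The concern.** Reporting under 9.6 starts only when someone becomes aware of a pregnancy, so ascertainment depends on finding it. A scheduled test does this at every treatment visit. A test taken the day after the last dose, however, cannot show a conception from the days just before it, and nothing is scheduled after it. Conceptions in the last days of dosing are therefore the on-treatment conceptions that meet no later scheduled test, even though the subject returns about four weeks later and gives blood.

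At stake is the completeness of safety data on pregnancies exposed to the drug. No efficacy endpoint or test is involved.

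**Working it through.** The plan gives no figure to reproduce here. The check compares the visit lists and then counts days.

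**1. Scheduled beta-HCG, from the tables**

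| Schedule | Treatment visits with beta-HCG | Follow-up visits with beta-HCG |
|---|---|---|
| Table 2 (Stage 2) | 4 of 4 (Visits 5 to 8) | 0 of 1 (Visit 9) |
| Table 3 (sub-study) | 5 of 5 (Visits 8 to 12) | 0 of 1 (Visit 13) |

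These rows are legible, and the list in 8.2.1.3 has no blacked-out item, so redaction does not explain the gap.

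**2. Timeline.** Let T be the day of the last dose.
- Exit beta-HCG: T+1.
- Follow-up counted from the end-of-treatment visit (8.2.1.3): T+1+28 = T+29, range T+22 to T+36.
- Follow-up counted from the last dose (8.1.1): T+28, or T+21 to T+35 if the same ±7 days applies.
- Earliest follow-up on either reading: T+21.
- End of the contraception and reporting period: T+60.

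**3. What the exit test misses.** Let L be the days from conception to a positive serum test. L is not in the documents; 7 to 14 is assumed. The exit test sees conceptions up to T+1−L and so misses the last L−1 dosing days.
- L = 7: sees up to T−6, misses T−5 to T, which is 6 days.
- L = 14: sees up to T−13, misses T−12 to T, which is 13 days.

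Any lag above one day leaves some gap.

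**4. Share of nominal ataluren dosing days.** The placebo arm starts ataluren at Week 48.

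| Completer | Ataluren days | 6 days missed | 13 days missed |
|---|---|---|---|
| Ataluren arm, parent study | 144 × 7 = 1008 | 0.60% | 1.29% |
| Ataluren arm, with sub-study | 240 × 7 = 1680 | 0.36% | 0.77% |
| Placebo arm, parent study | (144−48) × 7 = 672 | 0.89% | 1.93% |
| Placebo arm, with sub-study | (240−48) × 7 = 1344 | 0.45% | 0.97% |

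**5. What a follow-up test would see.** A test on day D sees conceptions up to D−L.
- Earliest, D = T+21: up to T+14 (L = 7) or T+7 (L = 14).
- Nominal, D = T+29: up to T+22 or T+15.

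All are after T. At D = T+21 the limit stays at or after T for any L up to 21, so every on-treatment conception still ongoing at the visit would be detected.

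**6. Illustration per woman.** Assume 5% to 10% pregnancies per woman-year, spread evenly over days (not in the documents).
- Low: 0.05 × 6/365 = 0.0008, or 0.08%.
- High: 0.10 × 13/365 = 0.0036, or 0.36%.

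**The case against.** The case against acting rests on five points.

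- **No contradiction.** Section 9.6 is triggered by awareness and promises no testing to day 60. That is correct, and the point is a design choice rather than a conflict. But when reporting depends on awareness, a scheduled test matters more.
- **The fix does not cover 60 days.** This is also correct. At nominal follow-up it reaches T+15 to T+22, and later conceptions stay untested. It closes the on-treatment gap only.
- **Other routes exist.** These include open-ended adverse event questions (9.2), physical examination at follow-up (8.2.1.3), tests prompted by clinical findings (8.3.12) and further evaluations at discontinuation (Section 10). Under 9.1.2, adverse pregnancy outcomes are serious adverse events, reportable after participation if the investigator hears of them. All of these depend on judgement or awareness. They reduce the loss but do not replace a test.
- **The expected number is tiny.** SAP 2.5 lowers the sample to 24. If all 24 were females of childbearing potential, the illustration gives 24 × 0.0008 = 0.02 to 24 × 0.0036 = 0.09 missed conceptions; with 36 subjects, 0.03 to 0.13. The enrolled population includes males and immature children, so on the same assumptions the figure would be lower. Protocol 13.1.2 and 14.1 also report no genotoxicity, no effect on rat fertility, no teratogenicity in rats or rabbits, and fetal toxicity only at doses toxic to the mother. This stands, and it is why the point is minor.
- **The Study Manual may cover it.** Section 9.6 refers to that manual, which was not available for review. If it does, the provision should also appear in the protocol.

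**Conclusion.** The point holds as a minor gap in safety ascertainment. For a completer, the last scheduled beta-HCG falls one day after the last dose, and the only later visit omits it. Under the assumed 7 to 14 day lag, conceptions in the last 6 to 13 dosing days go unseen by any scheduled test. That is 0.4% to 1.9% of nominal ataluren dosing days.

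The existence of the gap requires only a lag longer than one day; its size rests on the assumed range. The number of females of childbearing potential is not given, so no count of missed pregnancies is claimed. For a subject who stops early, the exit test can fall later after her last dose, so her gap may be shorter.

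**What to change.** Add serum beta-HCG for females of childbearing potential to the follow-up visit in Protocol Table 2 (Visit 9), Table 3 (Visit 13) and Section 8.2.1.3, with the SAP's copies of the tables updated to match. The cost is one assay per relevant subject on blood already being drawn, with no extra visit or needle, and a short amendment.

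Optional, in the same amendment: criterion 10 begins "Male subjects with partners of childbearing potential must agree to use adequate (at least 1 form of) contraception" and sets the same 60-day period, yet 9.6 asks for notification only when "a female subject in the study becomes pregnant at any time after" her first dose. One sentence extending notification to pregnant partners of male subjects would align the two. If the Study Manual already contains either provision, carry it into the protocol.
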